1.2.2 Treatments

Three treatment arms will be used in this cross-over study:-

- Super Poligrip Free (USA marketplace) applied via a conventional pattern.
- Super Poligrip Free (USA marketplace) applied via a continuous strips pattern.
- No adhesive.

A single, common adhesive will be used (Super Poligrip Free) with a common dose (1.6g) for both application methods. The adhesive will be extruded from a pre-dosed syringe following the application instructions. Super Poligrip Free has been selected as the adhesive in this study as it is a currently marketed product and is considered a representative denture adhesive. 1.6g of adhesive per treatment will be applied to each subject's dentures, an amount consistent with that used in previous studies and will therefore facilitate comparison of data from this study with previous work. This dose will be split as 1.00 ± 0.05 g for the maxillary and 0.60 ± 0.05 g for the mandibular dentures in accordance with consumer's normal distribution of adhesive.

A no adhesive negative control treatment has been chosen to provide a continual reference point to allow interpretation of the results and to facilitate comparison of the results from this

Document Name	208397 Clinical Protocol 2.docx	Document Identifier	Effective Date
Type	Version		
eldo_controlled	2.0; Most-Recent; Effective; CURRENT	090032d580db1b91	24-Oct-2017 08:49:05

Sodium-calcium mixed partial salt of poly(methylvinylether/maleic acid) and carboxymethylcellulose

208397

Final Clinical Protocol, 20 Oct 2017

study with previous work, and is representative of a significant number of denture wearers who currently do not use an adhesive.

Complete information for this compound may be found in the single reference safety document (SRSD), which for this study is the Safety Statement.

2 STUDY OBJECTIVES AND ENDPOINTS

Table 2-1 Study Objectives and Endpoints

Objectives	Endpoints
Primary	
To evaluate the mass of peanut particles that migrate under the dentures during a food occlusion methodology when denture adhesive is applied per conventional pattern.	Mass of peanuts under combined maxillary and mandibular dentures.
Exploratory	
To evaluate the mass of peanut particles that migrate under the dentures during a food occlusion methodology when denture adhesive is applied per continuous strips pattern and when no adhesive is used.	Mass of peanuts under combined maxillary and mandibular dentures.
To evaluate the mass of peanut particles that migrate under the maxillary and mandibular dentures during a food occlusion methodology when denture adhesive is applied per conventional pattern, continuous strips pattern and when no adhesive is used.	Mass of peanuts under maxillary dentures. Mass of peanuts under mandibular dentures.
To evaluate subject responses to 2 questions during a food occlusion methodology when denture adhesive is applied per conventional pattern, continuous strips pattern and when no adhesive is used.	Subject completed questionnaire.
To explore the performance of a marketed denture adhesive when applied per conventional pattern to no adhesive use for subjects in the low and high Kapur-Olshan subgroups.	Mass of peanuts under combined maxillary and mandibular dentures in each subgroup (low and high Kapur-Olshan scores).
To explore the relationship between the number of subject-reported denture dislodgements when denture adhesive is applied per conventional pattern, continuous strips pattern and when no adhesive is used.	The number of subject reported denture dislodgements during chewing.
Safety	
To assess the tolerability of marketed denture adhesive (Super Poligrip Free).	Treatment emergent adverse events.

This study is a method development study and therefore there is no formal success criterion.

Document Name	208397 Clinical Protocol 2.docx	Document Identifier	Effective Date
Type	Version		
eldo_controlled	2.0; Most Recent; Effective; CURRENT	090032d580db1b91	24-Oct-2017 08:49:05

Sodium-calcium mixed partial salt of poly(methylvinylether/maleic acid) and carboxymethylcellulose

208397

Final Clinical Protocol, 20 Oct 2017

3 STUDY DESIGN AND SUBJECT POPULATION

This will be a single centre, controlled, open label, randomised, three-treatment, three-period, cross-over design in subjects with full upper and full lower dentures. Each treatment period will consist of one day of testing with at least two days between adjacent treatment visits.

Approximately 48 (maximum 50) healthy subjects with both maxillary and mandibular full dentures will be enrolled in this study. In this study, subject recruitment will be targeted to achieve approximately equal numbers of subjects in the low and high Kapur-Olshan groups. The low Kapur-Olshan group is defined as a composite Kapur-Olshan score of 6-14 (clinically fair and good dentures) and the high Kapur-Olshan score as 15-18 (clinically very good dentures).

At the screening visit, following an OST examination, each subject's dentures (upper and lower) will be cleaned then assessed for retention and stability using the Kapur Index (Olshan Modification) ([Kapur, 1967](#); [Olshan, 1992](#)) and whether they are well made. Only those subjects with dentures (both upper and lower) that satisfy both of these criteria will undergo the food migration adequacy assessment to provide evidence of adequate peanut particle migration under the dentures after chewing a portion of peanuts. A visual observation and rating of location and extent of peanut particle migration adequacy must indicate > 0 on a 0 – 3 scale. Subjects meeting all the inclusion criteria with no exclusions will then be randomised at Visit 2. Subject recruitment will be controlled to ensure 50±10% of the subjects will be in each of the low and high Kapur-Olshan groups [the low Kapur-Olshan group is defined as a composite Kapur-Olshan score of 6-14 (clinically fair and good dentures) and the high Kapur-Olshan score as 15-18 (clinically very good dentures)]. There will be between 2-30 days between the screening visit and the for test day.

On each test day (Visits 2-4) subjects will undergo an OST examination and have their dentures cleaned. Treatment (or no treatment as per the randomisation schedule) will then be applied as per the application instructions and the dentures worn by the subject. Then, 60±5 minutes after inserting their dentures each subject will be given a standardised portion of peanuts to consume, following a prescribed chewing and swallowing method. Whilst chewing the peanuts subjects will record the number of denture dislodgements that occur during the chewing procedure. After this, subjects will rinse their mouth with water. The examiner will then remove the lower denture and any peanut particles or adhesive remaining on the mandibular ridge will be removed using gauze. The examiner will then remove the upper denture and any peanut particles or adhesive remaining on the palate will be removed using new gauze. The subject will then complete a questionnaire on efficacy and a further OST examination will be performed.

For a subset of subjects the fit surface of their dentures will be photographed before peanuts are collected from the fit surface. These subjects will be selected at the discretion of the Investigator, but allow for a variety of denture sizes and fit to be represented. It is expected that approximately 5 sets of dentures be photographed per treatment group, and where possible that consistency of subjects between treatments is maintained (i.e. a subject will be identified at visit 2 as being suitable for denture imaging and will have their dentures

Document Name	208397 Clinical Protocol 2.docx	Document Identifier	Effective Date
Type	Version		
eldo_controlled	2.0; Most-Recent; Effective; CURRENT	090032d580db1b91	24-Oct-2017 08:49:05

Sodium-calcium mixed partial salt of poly(methylvinylether/maleic acid) and carboxymethylcellulose

208397

Final Clinical Protocol, 20 Oct 2017

photographed at visits 2, 3 and 4 however, should subject dropouts or other reasons necessitate, subjects can be substituted).

Peanut particles will then be collected from the fit surfaces of the dentures and the gauzes and weighed to evaluate the mass of food particles that had migrated under the denture (keeping the particles associated with the upper and lower dentures separate).

These procedures will be repeated in a crossover manner. There will be between 2-30 days between treatment visits to allow for recovery from the mastication procedures.

Safety will be assessed by examination of the oral soft tissues at the Screening Visit and before and after each treatment assessment has been completed at each of the treatment visits. Abnormalities reported after the subject's first use of treatment will be considered as adverse events (AEs). Incidents will be recorded from the first use of a medical device.

4 SUBJECT SELECTION

This study can fulfil its objectives only if appropriate subjects are enrolled. The following eligibility criteria are designed to select subjects for whom participation in the study is considered appropriate. All relevant medical and nonmedical conditions should be taken into consideration when deciding whether a particular subject is suitable for this protocol.

4.1 Inclusion Criteria

Subject eligibility should be assessed and documented by an appropriate member of the investigator's study team before subjects are enrolled in the study.

Subjects must meet all of the following inclusion criteria to be eligible for enrolment into the study:

- 1) Evidence of a personally signed and dated informed consent document indicating that the subject has been informed of all pertinent aspects of the study before any assessment is performed.
- 2) Male or female who, at the time of screening, are between the ages of 18 and 85 years, inclusive.
- 3) Willing and able to comply with scheduled visits, treatment plan, and other study procedures.
- 4) Healthy, defined as in general good physical health, as judged by the investigator.
- 5) Self-reports experience of getting food trapped under their denture.
- 6) Is an habitual wearer of both of their dentures defined as subjects who wear both of their dentures for the majority of their time whilst awake.
- 7) Females of childbearing potential and at risk for pregnancy must agree to use a highly effective method of contraception throughout the study and for 1 day after the last dose of assigned treatment. Female subjects who are not of childbearing potential must meet requirements in [Section 4.4.2](#).
- 8) Have denture prostheses that fulfil all of the following:

 GlaxoSmithKline	Document Name	208397 Clinical Protocol 2.docx	Document Identifier	Effective Date
	Type	Version		
	eldo_controlled	2.0; Most Recent; Effective; CURRENT	090032d580db1b91	24-Oct-2017 08:49:05
	Reason For Issue	Auto Issue		

Sodium-calcium mixed partial salt of poly(methylvinylether/maleic acid) and carboxymethylcellulose

208397

Final Clinical Protocol, 20 Oct 2017

- a) A qualifying conventional acrylic full denture in both the upper and lower arch.
- b) Dentures are well fitting (Kapur (Olshan Modification) Retention and Stability Index Sum Score ≥ 6) ([Olshan, 1992](#)) with no individual stability or retention scores < 1 .
- c) Dentures are well made (according to the well-made assessment).
- d) Has a peanut particle migration rating > 0 for each denture.

4.2 Exclusion Criteria

Subjects who meet any of the following exclusion criteria will not be eligible for enrolment in the study:

1. An investigational site staff member directly involved in the conduct of the study or their family member, site staff members otherwise supervised by the investigator, or an employee of the sponsor directly involved in the conduct of the study.
2. Participation in any other clinical study involving investigational drugs, cosmetics or medical devices within 30 days prior to study entry and/or during study participation.
3. Acute or chronic medical or psychiatric condition or laboratory abnormality that may increase the risk associated with study participation or investigational product administration or may interfere with the interpretation of study results and, in the judgment of the investigator, would make the subject inappropriate for entry into this study.
4. Pregnant female subjects.
5. Breastfeeding female subjects.
6. Known or suspected intolerance or hypersensitivity to the study materials (or closely related compounds) or any of their stated ingredients.
7. Unwilling or unable to comply with the Lifestyle Guidelines described in this protocol.
8. History of swallowing difficulties or choking.
9. Currently taking or have taken a bisphosphonate drug (i.e., Fosamax®, Actonel®, Boniva®) for treatment of osteoporosis.
10. Any clinically significant or relevant oral abnormality (e.g. temporomandibular joint [TMJ] problems) that, in the opinion of the investigator, could affect the subject's participation in the study.
11. Known allergy to peanuts or any other nut.
12. Any condition or medication which, in the opinion of the investigator, is currently causing xerostomia.
13. Recent history (within the last year) of alcohol or other substance abuse.
14. OST examination findings such as stomatitis, open sores, lesions, redness or swelling which in the opinion of the investigator, would interfere with the conduct of the study.

[®] Fosamax is a registered trademark of Merck & Co.

[®] Actonel is a registered trademark of Warner Chilcott Company, LLC.

[®] Boniva is a registered trademark of Genentech.

 GlaxoSmithKline	Document Name	208397 Clinical Protocol 2.docx		
	Type	Version	Document Identifier	Effective Date
	eldo_controlled	2.0; Most Recent; Effective; CURRENT	090032d580db1b91	24-Oct-2017 08:49:05
	Reason For Issue	Auto Issue		

Sodium-calcium mixed partial salt of poly(methylvinylether/maleic acid) and carboxymethylcellulose

208397

Final Clinical Protocol, 20 Oct 2017

15. Use of any medication that, in the opinion of the investigator, would interfere with the conduct of the study.
16. A serious chronic disease requiring intermittent hospital visits.
17. Having been previously enrolled in this study.
18. Any subject who, in the opinion of the investigator, should not participate in the study.

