In order for subjects to be eligible they must report that they get food trapped under their dentures and this must be evident following the standardised peanut migration adequacy testing at screening (Visit 1). This is to ensure that measurable amounts of peanut particles migrate under the denture when no denture adhesive is being used. Whilst peanut allergy is specific, peanuts supplied for this study may themselves be contaminated with other nuts owing to the manufacturing process. Therefore, subjects with any nut allergy are excluded from this study. Subjects with temporomandibular joint disorders are excluded should the investigator believes that this could affect the subject's participation, principally regarding the ability for the subject to adequately chew the peanuts. Subjects who use or have ever used bisphosphonate medications are specifically excluded from this study owing to the enhanced risk of bisphosphonate-related osteonecrosis of the jaw (BRONJ) that is associated with reduced tissue tolerance to function with removable prostheses ([Saldanha, 2012](#)). Subjects in this study must be habitual wearers of full dentures to ensure that they are familiar with chewing with their dentures in place. Subjects who are xerostomic are excluded since the proper function of denture adhesives requires adequate hydration from saliva.

During this study, photographs of dentures with peanut particles attached will be taken. The purpose of this is to gather representative photographs of the dentures to aid in the dissemination and interpretation of the results, e.g. in manuscript preparation. No personally identifiable information will be included in these photographs. Demography information will be recorded as part of this study, including age, race and gender. In accordance with the United States Food and Drug Administration (US FDA) guidelines ([FDA, 2005](#)) the ethnicity of subjects will also be captured.

An oral soft tissue (OST) examination will be conducted at each treatment visit before treatment is applied to ensure the subject's oral health is sufficient to allow the subject to complete the assessments at that visit. A further OST exam will be performed at each treatment visit after the completion of assessments to assess for possible AEs.

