4.4 Lifestyle Guidelines

During the entire study (screening – LSLV):

- Subjects will not be permitted to have any dental/denture work performed during the time they are in the study, unless discussed and permitted by the examiner. This is to assure that the denture fit will not be altered during the study.
- Subjects are not permitted to use of bisphosphonates as per exclusion criterion 9.

During the treatment visits (Visits 2-4):

- Subjects will not be allowed to use tobacco or nicotine-containing products following denture insertion until after their dentures are returned at completion of the food occlusion testing.
- Subjects will not be able to use any oral healthcare product other than those supplied by the investigator following denture insertion until after their dentures are returned at completion of the food occlusion testing.

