5.7 Concomitant Treatments

Details of any relevant dental, medical or surgical history (within the last year), including allergies or drug sensitivity, will be recorded in the CRF. The use of concomitant medications is permitted in this study with the exception of the use of bisphosphonate drugs (exclusion criterion 9) and medications that in the opinion of the investigator would interfere with the conduct of this study (exclusion criterion 15).

Treatments taken after the first dose of study investigational product will be documented as concomitant treatments.

All concomitant treatments taken during the study must be recorded with indication, unit dose, daily dose, and start and stop dates of administration. All subjects will be questioned about concomitant treatment at each clinic visit.

Subjects will be asked not to have any non-emergency dental/denture work performed during the time they are in the study, unless discussed and permitted by the examiner. This is to assure that the denture fit will not be altered during the study.

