6 STUDY PROCEDURES

6.1 STUDY PERIOD

6.1.1 Screening - Visit 1

The following procedures/assessments will take place in the order listed below (where possible), and recorded in the CRF:

- Obtain written informed consent.
- Collect demography (year of birth, gender, race and ethnicity).
- Obtain medical history, including history of illegal drug, alcohol and tobacco use.
- Obtain [Dental History](#).
- Obtain complete medication history of all prescription or non-prescription drugs, and dietary and herbal supplements taken within 30 days prior to the planned first dose.
- Perform [OST Examination-Edentulous](#).
- Clean the subject's dentures using the supplied denture brush and cleansing paste, both the upper and lower dentures will be thoroughly cleaned to remove all traces of denture fixative, plaque and particulates/debris. Dentures should then be dried.
- Perform the [Well-Made Assessment](#).
- Perform the [Well-Fit Assessment](#).
- Perform the [Food Migration Adequacy Assessment](#).
- Review Inclusion and Exclusion criteria. Pregnancy status will be confirmed verbally by the subject.
- Assess subject eligibility.
- Any serious adverse event assessed as related to study participation that occurs subsequent to the signing of informed consent will be recorded.

To prepare for study participation, subjects will be instructed on the use of the [Lifestyle Guidelines](#) and [Concomitant Treatment\(s\)](#) sections of the protocol.

6.1.2 Visit 2

Subjects will be admitted to the clinical site between 2-30 days after Screening. The following procedures will be completed in the following order (wherever possible) and recorded in the CRF:

- Review Inclusion and Exclusion criteria. Pregnancy status will be confirmed verbally by the subject.
- Collect urine pregnancy test for females of childbearing potential.
- Confirm proper contraception is being used.
- Review changes in the subject's medical history including medication history since Screening.
- Perform [OST Examination-Edentulous](#).

 GlaxoSmithKline	Document Name	208397 Clinical Protocol 2.docx		
	Type	Version	Document Identifier	Effective Date
	eldo_controlled	2.0; Most Recent; Effective; CURRENT	090032d580db1b91	24-Oct-2017 08:49:05
	Reason For Issue	Auto Issue		

Sodium-calcium mixed partial salt of poly(methylvinylether/maleic acid) and carboxymethylcellulose

208397

Final Clinical Protocol, 20 Oct 2017

- Assess subject eligibility.
- Randomise subject to treatment group.

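### Exclusion criterion 9 limits the bisphosphonate exclusion to osteoporosis treatment, so it misses users for other indications, chiefly past ones, whom the safety rationale says are excluded

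*Protocol*

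**What the plan says.** The rationale in Protocol 1.2.1 is explicit: "Subjects who use or have ever used bisphosphonate medications are specifically excluded from this study owing to the enhanced risk" of osteonecrosis of the jaw, which it ties to poorer tissue tolerance of removable prostheses. It sets no limit by indication, brand or time since use.

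Criterion 9 in Protocol 4.2 excludes subjects "Currently taking or have taken a bisphosphonate drug", then gives three brands after *i.e.* and ends with "for treatment of osteoporosis".

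Two other places mention the drug class, and both concern use during the study. Section 4.4 says "Subjects are not permitted to use of bisphosphonates as per exclusion criterion 9". Section 5.7 permits concomitant medication "with the exception of the use of bisphosphonate drugs (exclusion criterion 9") and of drugs the investigator thinks would interfere. Criterion 7 excludes anyone "Unwilling or unable to comply with the Lifestyle Guidelines described in this protocol", which gives the Section 4.4 bar some force at entry.

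On history taking, Section 6.1.1 asks at Visit 1 for a "complete medication history of all prescription or non-prescription drugs, and dietary and herbal supplements taken within 30 days" of the planned first dose. Section 5.7 has the CRF record "Details of any relevant dental, medical or surgical history (within the last year").

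**The concern.** The hazard in Section 1.2.1 comes from the drug combined with the prosthesis. Nothing in the protocol suggests that it depends on why the drug was prescribed, yet criterion 9 makes eligibility depend on that. The *i.e.* can also be read as making the three brands a closed list, which would narrow the rule further.

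The criterion is what governs entry. Under Sections 4.3 and 5.1, a subject who meets every inclusion criterion and no exclusion criterion is randomised. A past user with another indication passes criterion 9 as worded. Enrolling that person would not breach the criterion, so the eligibility check among the major deviations in SAP 4.1.2 would not flag it either.

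What is at stake is subject safety. The point has no bearing on the endpoints, the analysis populations or the statistical methods.

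**Working it through.** No sample size, power or error rate is involved, so the check is a comparison of texts, plus a short count of exposure.

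**Who is excluded, by category**

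| Bisphosphonate use | Section 1.2.1 | Criterion 9 | Other provisions |
|---|---|---|---|
| Current or past, for osteoporosis | Excluded | Excluded | Not needed |
| Current, other indication | Excluded | Not covered | Arguably barred by 4.4 with criterion 7, and by 5.7; both sections point back to criterion 9 |
| Past, other indication | Excluded | Not covered | No specific exclusion |

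The third row is a clear gap and the second a partial one.

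**What else could stop a past user with another indication**

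- Criteria 3, 10, 15 and 18, and inclusion criterion 4 (general good health), rest on the investigator's judgement.
- Criterion 16 is categorical, but applies only to a serious chronic disease that needs intermittent hospital visits.
- Criterion 14 and the oral soft tissue examinations respond to visible findings, not to drug exposure.

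None of these delivers the specific exclusion that Section 1.2.1 describes.

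**Whether the recorded histories would reveal it**

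The Visit 1 medication history looks back 30 days, and the relevant history in Section 5.7 looks back one year. The separate medical history item in Section 6.1.1 has no stated time limit, but it does not ask about bisphosphonates, and neither does the dental history in Section 7.1.2. Criterion 9 is therefore the only explicit prompt about past exposure, and its wording lets a person treated for another condition answer no.

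**Exposure per affected subject**

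- Peanut sessions in the study: one at screening (Section 7.1.5) and one at each of Visits 2, 3 and 4 (Section 7.2.1), so 1 + 3 = 4.
- Mass per session: 30 to 32 g.
- Sessions a corrected criterion would prevent: Visits 2 to 4, so 3 of the 4.
- Mass: 3 × 30 g = 90 g, to 3 × 32 g = 96 g.

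The screening session is not counted, because Section 6.1.1 lists the peanut adequacy assessment before the review of inclusion and exclusion criteria.

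**The case against.** The strongest reply is that the intent is plain and the affected group small. Three of the four mentions of bisphosphonates carry no limit by indication, and Sections 4.4 and 5.7 treat criterion 9 as if it covered the class. Monitors go through the protocol with site staff before the study starts (Section 11.1). An investigator who learns of past use has the rationale in hand and can invoke criterion 18. What remains is a past user, treated only for something else, judged healthy and free of serious chronic disease, in a study capped at 50 subjects. This limits the likely consequence. It does not close the gap, because criterion 18 is discretionary and the rationale promises a specific exclusion.

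Several narrower points stand. Peanut mass counts exposure and does not measure harm: every subject already wears both dentures habitually, the documents do not show how much risk three supervised sessions add, and soft tissue examinations come before and after each treatment session. The short look-back periods apply equally to past osteoporosis users, so they are not peculiar to this gap. Inserting *ever* is mainly for clarity, since the existing wording on past use has no time limit.

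It is also argued that if the histories cannot reveal remote use, rewording the criterion will not reveal it. That goes too far. Criterion 9 already obliges the site to establish past use, and the corrected wording works through the same review by removing the indication as a reason to pass. The fix depends on neither the look-back periods nor the peanut mass.

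**Conclusion.** The concern holds. Criterion 9 is wrong as written: it does not deliver the exclusion that Section 1.2.1 states on safety grounds. The defect is clear for past users treated for an indication other than osteoporosis and partial for current ones.

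The number of subjects affected cannot be estimated, because the documents give neither a prevalence nor any other indication for these drugs. Among approximately 48 healthy subjects it may be few or none. The per-subject exposure above assumes that such a person would reveal past use when asked under the corrected criterion, and that the investigator would not already have excluded them at discretion.

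This should be corrected, because a stated safety rule falls short of its own rationale and the remedy is simple. The absence of any statistical consequence and the likely small numbers argue against a higher grade.

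**What to change.** In criterion 9 of Protocol 4.2, delete "for treatment of osteoporosis", insert *ever* before *taken*, and change *i.e.* to *e.g.* before the brand names. The criterion then covers current or any past use of any bisphosphonate for any indication, with the brands as examples. Sections 1.2.1, 4.4 and 5.7 then agree with it without further edits.

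A direct question on lifetime bisphosphonate use at Visit 1 would help detection and is worth adding, although the correction does not depend on it.

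The cost is a one-line protocol amendment with IRB approval under Section 11.3.1, and possibly a few more screen failures, whose number the documents do not allow one to estimate. The Schedule of Activities already has the criteria reviewed at every visit, so the new wording would take effect through existing procedures. It would not reliably spare an affected person the screening peanut session, because of the order of procedures in Section 6.1.1.
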